7.4. Laboratory Procedures

The optical bench will be used to measure the light transmission characteristics for all worn Test lenses. The findings are for internal information only and will not be part of the final report.

8. SUBJECTS COMPLETION/WITHDRAWAL

8.1. Completion Criteria

The disposition (accountability) of all enrolled subjects will be presented by study lens and overall to show the number and percentage of subjects in each of the following status subgroups:

1. Completed: Subjects are considered to have completed the study if they have completed all scheduled visits.
2. Discontinued: Subjects are considered to have discontinued from the study if they are (i) randomized (ii) Successfully Dispensed and (iii) discontinued because of one of the following reasons: a) Withdrew Consent (b) Lost to Follow Up (c) Subject no longer meets eligibility criteria (e.g. pregnancy) (d) Subject withdrawn by PI due to non-compliance to protocol (e) Discontinuation of study treatment as a result of the investigator's belief that for safety (f) Reasons it is in the best interest of the subject to stop treatment (g) Study lens no longer available (h) A scheduled visit was missed.
3. Total dispensed: Completed + Discontinued
4. Enrolled not Successfully Dispensed: Subjects are considered to be Enrolled Not Successfully Dispensed Subjects if they were (i) enrolled to the study (provided informed consent) but failed to satisfy the eligibility criteria (inclusion/exclusion criteria), (ii) were not randomized to study lens for any reason or (iii) if they are randomized but did not satisfactorily complete the dispensing process. This includes subjects who were dispensed a different type of study lens for each eye or who were dispensed same study lens for both eyes but did not return for any follow-up visits.
5. Total enrolled: Completed + Discontinued + Enrolled not Successfully Dispensed
6. The percentage will be calculated using total enrolled as denominator.
7. Safety and efficacy analysis sets will be defined as subsets of dispensed subjects (Completed + Discontinued).

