Wear and Replacement Schedules	Wear Schedule: daily wear (DW) Replacement Schedule: approximately 2 weeks
Objectives	The primary objective of this study is to demonstrate non-inferiority of the Test lens compared to the Control lens with respect to CLUE comfort, Slit Lamp Findings and Monocular logMAR Distance Visual Acuity. This study will also aim to show the Fit Acceptance rate is at least 90% in order to assess performance of the Test lens for eventual Design Validation and/or Claims studies.
Study Endpoints	Primary Endpoints: 
• Monocular logMAR distance visual acuity• Biomicroscopy• Fit acceptance rate• Overall CLUE comfort Secondary Endpoints: 
• Overall CLUE vision• Overall CLUE handling

[figure not shown]
Study Design	
This study is a randomized, 5-visit, partial subject-masked, 2×3 bilateral crossover, dispensing trial. The study lenses will be worn as daily wear (DW) for a period of 2 weeks each with one of the study lenses being worn twice. Each study lens is expected to be worn at least five (5) days per week for at least six (6) hours per day worn. There will be no washout period between study lenses.
 
See the flow chart at the end of the synopsis table for the schematic of the study visits and procedures of main observations.

Sample Size	
Approximately 130 eligible subjects will be enrolled and randomized into the study. Approximately 120 subjects are targeted to complete the study. A replacement subject may be enrolled if a subject discontinues from the study prematurely; the decision whether to enroll replacement subjects will be made by the joint agreement of the Investigator and Sponsor.

Study Duration	
Subjects will wear the Test and control lenses for 2 weeks each in random order with one of the study lenses being worn twice for a total of 6 weeks per subject. The enrollment period will be 2 weeks, making the entire study approximately 8 weeks in duration.

Anticipated Study Population	
Approximately 130 subjects will be enrolled to ensure that at least 120 subjects will complete the study. Enrolled subjects will be habitual wearers of spherical contact lenses. All subjects will be the age of ≥ 18 and ≤ 49.

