14.9. Procedure for Handling Missing Data and Drop-Outs

Missing or spurious values will not be imputed. The count of missing values will be included in the summary tables and listings.

Subject dropout is expected to be one of the main reasons of missing data in this clinical trial. Past clinical trials don't provide the evidence that subject dropout is systematic or not-at-random. To evaluate the impact of missing data, sensitivity analysis will be conducted using multiple imputation methods if the proportion of subject dropout is greater than the 15%. The

SAS/STAT procedures PROC MI and PROC MIANALYZE will be utilized with a parametric regression method used to make at least 10 imputations.

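### Section 8.1 counts subjects who took study lenses home and never returned as not dispensed, and divides by everyone who consented, so the overall discontinuation percentage can only equal or understate loss among randomised subjects

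*Combined protocol and SAP*

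**What the plan says.** Section 8.1 sets out the disposition table. It opens: "The disposition (accountability) of all enrolled subjects will be presented by study lens and overall". The relevant rules are these.

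- **Item 2 (Discontinued).** The definition runs: "Subjects are considered to have discontinued from the study if they are (i) randomized (ii) Successfully Dispensed and (iii) discontinued because of one of". What comes next there is a list of reasons, which includes loss to follow-up (b) and a missed scheduled visit (h). It has no entry for unacceptable lens fit found after dispensing.
- **Item 4 (Enrolled not Successfully Dispensed).** This class takes subjects "enrolled to the study (provided informed consent) but failed to satisfy the eligibility criteria (inclusion/exclusion criteria"), subjects never randomised, and randomised subjects whose dispensing was not satisfactorily completed. The last group expressly includes those who were "dispensed same study lens for both eyes but did not return for any follow-up visits".
- **Item 5.** "Total enrolled: Completed + Discontinued + Enrolled not Successfully Dispensed".
- **Item 6.** "The percentage will be calculated using total enrolled as denominator".

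The synopsis uses the word enrolled differently: "Approximately 130 eligible subjects will be enrolled and randomized into the study", with about 120 targeted to complete.

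Section 8.2 lists both loss to follow-up and any missed scheduled visit as grounds for withdrawal, without requiring that the subject came back at least once.

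Section 14.9 plans a multiple-imputation sensitivity analysis "if the proportion of subject dropout is greater than the 15" per cent. It does not say how that proportion is formed.

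**The concern.** A subject who was randomised, met the Visit 1 continuance criteria (step 1.24), went home with study lenses and was never seen again is lost to follow-up in the ordinary sense. Under item 4 that subject shares a row with people who never met the entry criteria. The Discontinued row does not include the loss, and the pooled row does not let a reader recover it.

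This group matters because these subjects have been exposed only to their first assigned lens and left before any follow-up. Lens-related departure could appear there, and masking is only partial (section 5.2). In a non-inferiority trial, readers use the disposition table to judge whether subjects left because of the Test lens.

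The denominator adds to the effect. Recruiting more ineligible people lowers the reported discontinuation percentage without changing how many randomised subjects were lost.

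**Working it through.** **Plan's own figures.** No discontinuation rate is stated, so there is none to reproduce. The planned 130 randomised and 120 completing imply (130 − 120)/130 = 7.7% loss.

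**Definitions.** R = subjects randomised; D = randomised subjects who do not complete; k = randomised subjects dispensed lenses who never return; s = consented subjects not randomised. R and the planning value of D come from the synopsis. The plan gives neither k nor s, so both are assumed below. Randomised subjects never dispensed a lens are set to zero; item 4 would also keep them out of Discontinued, which acts in the same direction.

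**Direction.**

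- Loss among randomised subjects = D/R
- Section 8.1 percentage = (D − k)/(R + s)

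Since k ≥ 0 and s ≥ 0, the second can never exceed the first. They are equal only if k = s = 0, or if D = 0.

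**Size at the planning numbers (R = 130, D = 10; loss 7.7%).**

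| Assumed k | s = 0 | s = 20 | s = 33 |
|---|---|---|---|
| 0 | 10/130 = 7.7% | 10/150 = 6.7% | 10/163 = 6.1% |
| 3 | 7/130 = 5.4% | 7/150 = 4.7% | 7/163 = 4.3% |
| 5 | 5/130 = 3.8% | 5/150 = 3.3% | 5/163 = 3.1% |

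**By lens.** Assume 65 subjects per sequence and 5 losses on the first-worn lens, 2 of them never-returners. Loss is 5/65 = 7.7%. The section 8.1 count is 3. That gives 3/65 = 4.6% if the column uses that lens's own subjects, and 3/150 = 2.0% if it uses all enrolled with s = 20. Section 8.1 does not say which applies. The drop from 5 to 3 follows from item 4; the denominator is open.

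**The 15% trigger, only if section 14.9 is read through section 8.1.** Total enrolled = 130/(1 − screen-failure proportion). The smallest Discontinued count above 15% of that, plus k, is the number of actual leavers needed.

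| Assumed screen failure | Total enrolled | 15% of it | Smallest count above | Leavers, k = 0 | Leavers, k = 5 |
|---|---|---|---|---|---|
| 0% | 130 | 19.5 | 20 | 20 (15.4% of 130) | 25 (19.2%) |
| 10% | 144.4 | 21.7 | 22 | 22 (16.9%) | 27 (20.8%) |
| 20% | 162.5 | 24.4 | 25 | 25 (19.2%) | 30 (23.1%) |

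As an example, take 24 of 130 leaving (18.5%), 4 of them never-returners, with 14 screen failures. Section 8.1 gives (24 − 4)/(130 + 14) = 20/144 = 13.9%, below the trigger. Both conditions are needed: 14 screen failures alone give 24/144 = 16.7%, and 4 never-returners alone give 20/130 = 15.4%, each above 15%.

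**The case against.** The classification is explicit and set in advance. Item 2 applies its three conditions jointly, so its loss-to-follow-up reason covers only subjects who count as successfully dispensed; items 2 and 4 do not formally contradict each other. Never-returners are not deleted from the table. Counts appear beside percentages, and Total dispensed has its own row. Step F.1 records each reason for discontinuation, section 8.2 requires documented attempts to trace lost subjects, and section 14.9 requires counts of missing values. This stands, and it limits the harm. It does not separate never-returners from screen failures in the pooled row, nor alter the overall percentage.

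Four stronger readings are tempting, and the documents do not support them.

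- *That never-returners are not tied to any lens.* Section 8.1 presents every status subgroup by lens, and these subjects have a first lens, so they can appear under it.
- *That the by-lens denominator is wrong.* Screen failures have no lens and need not fall in a lens column. The denominator is unspecified, which is a lesser fault.
- *That section 8.1 governs the 15% trigger.* Section 14.9 never cites section 8.1. Section 14.3 also announces a separate SAP that would take precedence and could define dropout.
- *That poor vision and poor comfort are also missing discontinuation reasons.* The follow-up steps (2.8, 3.9, 4.9 and 5.8) discontinue for unacceptable fit only. Section 8.2 names vision and comfort only for subjects not successfully dispensed. Even for fit, step 5.8 falls at the last scheduled visit, where the subject may already count as Completed under item 1.

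**Conclusion.** The point holds as a reporting fault of modest weight. Items 2 and 4 to 6 yield an overall Discontinued percentage that can equal but never exceed loss among randomised subjects. By lens, the numerator is understated for the first-worn lens whenever a subject on it never returns; the denominator needs defining.

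The size cannot be fixed from the documents. It is zero if every dispensed subject returns at least once and nobody fails screening. The range of 20 to 30 leavers for the 15% trigger rests on the assumed 0–20% screen failure and 0–5 never-returners, and on a reading of section 14.9 that its text does not state. The 24-leaver example is also well above the 10 losses the plan expects. A missed trigger would omit a sensitivity analysis. By this route no sample size, power, margin, significance level or primary estimate changes.

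**What to change.** In section 8.1:

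- Class a subject who was dispensed study lenses and never returned as Discontinued (lost to follow-up), under the lens dispensed.
- Use subjects randomised as the overall denominator and subjects dispensed that lens as the by-lens denominator.
- Show screen failures as a separate count, outside the percentages.
- Add unacceptable fit after dispensing to the item 2 reasons, so that the table matches the follow-up steps.

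In section 14.9, define dropout as (randomised − completed)/randomised. At the planning numbers this is 10/130 = 7.7%, whatever the numbers of never-returners and screen failures.

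The reclassification also eases a tension. Item 7 draws the safety and efficacy sets from Completed plus Discontinued, which now leaves never-returners out. Section 14.3 would admit them to the Safety and ITT populations if at least one observation was recorded, and Visit 1 records symptoms, acuity and fit on the study lens.

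The cost is wording in two sections and one table shell. No new data are needed and no clinical procedure changes. The reported dropout becomes somewhat less favourable.

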1.23	Subjective Lens Fit Assessment	
Subjective Assessment of the Lens Fit. If the fit is graded as unacceptable based on the criteria below, then the subject is discontinued from the study and will not be replaced.
 
 1. Limbal exposure in any gaze 2. Edge lift 3. Insufficient and/or excessive movement in all three movement categories
1.24	Continuance	
For the subject to continue in the study, they must meet all three of the following criteria:
 
 1. Snellen visual acuity is 20/30 or better OD and OS 2. The lens fit is acceptable OD and OS 3. Investigator approval. If the Investigator does not approve the dispensing of the first study lens, then the study is terminated for that subject.
1.25	Dispense	
The lenses will be dispensed for 6-8 days
 
 1. The subjects should wear their lenses similar to the inclusion criteria: ≥ 6 hours

Visit 1: Treatment 1 Lens Fitting		
Step	Procedure	Details
		
per day, ≥ 5 days per week.
 
 2. The lenses will be worn as daily wear only. 3. All subjects will be provided Opti-Free® PureMoist® to be used in a rub regime. 4. Preservative-free rewetting drops are permitted if needed. 5. A patient instruction booklet will be provided. 6. The lenses must be stored in the supplied case out of direct sunlight. 
Note 1: In the event a lens is lost or damaged, the subject will return to the investigator site for replacement (extra lenses cannot be given at the dispensing visit).
 
Note 2: The subject's habitual contact lenses cannot be worn at any time during the study.

VISIT 2

The follow-up will occur 6-8 days after the initial dispensing. The subjects must enter the visit wearing their study contact lenses.

Visit 2: Treatment 1 Follow-Up 1		
Step	Procedure	Details
2.1.	Adverse Events and Concomitant Medications Review	
Review the subject's concomitant medications and record any changes from the previous study visit.
 
Record any adverse events or medical history changes from the previous study visit.

2.2.	Wearing Time	Record the average wearing time and comfortable wearing time.
2.3.	Compliance	Confirm compliance with the prescribed wear schedule. Outdoor and total hours will be asked.
2.4.	Subject Reported Ocular Symptoms	Subjects will respond to a verbal open-ended symptoms questionnaire.

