8.2. Withdrawal/Discontinuation from the Study

A subject will be withdrawn from the study for any of the following reasons:

- Subject death during the study period
- Subject withdrawal of consent
- Subject not compliant to protocol (e.g. Subject more than 2 days out of visit window).
- Subject lost to follow-up
- Subject no longer meets eligibility criteria (e.g. the subject becomes pregnant)

- Subject develops significant or serious adverse events causing discontinuation of study lens wear (subjects missing more than 2 days of missed lens wear within a period 1 of week should be discontinued)
- Subjects who have experienced a Corneal infiltrative Event (CIE)
- Investigator's clinical judgment regarding the subject safety reasons (that it is in the best interest of the subject to stop treatment)
- Subject missed any scheduled study visits
- Subject not compliant with study lens wear schedule
- Subject not successfully dispensed due to lack of efficacy and safety including poor vision, poor comfort or unacceptable fit

For discontinued subjects, the Investigator will:

- Complete the current visit (scheduled or unscheduled)
- Complete the Final Evaluation, indicating the reason that the subject was discontinued from the study
- Record the spherocylindrical refraction with best corrected distance visual acuity
- Collect used test article(s) (worn or brought to the visit) from the subject and discard them, unless otherwise stated in Section 0
- Collect all unused test article(s) from the subject

Investigator will discuss with sponsor before enrolling any additional subjects if a subject discontinues from the study prematurely.

In cases where a subject is lost to follow-up, every possible effort must be made to contact the subject and determine the reason for discontinuation/withdrawal. The measures taken to follow up must be documented including two written attempts and a certified letter (or equivalent) as the final attempt.

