14.3. Analysis Populations

A separate Statistical Analysis Plan (SAP) will be provided for this study. If there are any discrepancies between the protocol and the SAP, the SAP will supersede the statistical sections in the protocol.

Safety Population:

All subjects who were administered any test article excluding subjects who drop out prior to administering any test article. At least one observation should be recorded.

Per-Protocol Population:

All subjects who have successfully completed all visits and did not substantially deviate from the protocol as determined by the trial cohort review committee prior to database hard lock (Per-Protocol Population). Justification of excluding subjects with protocol deviations in the per-protocol population set will be documented in a memo to file.

Intent-to-Treat (ITT) Population:

All randomized subjects regardless of actual treatment and subsequent withdrawal from study or deviation from protocol. At least one observation should be recorded.

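### Section 8.1 item 7 excludes at least the randomised Test-first subjects who fail the Test fit at Visit 1, the 14.3 Safety and ITT definitions keep them, and 14.5 names no population for the primary fit test

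*Combined protocol and SAP*

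**What the plan says.** Subjects are randomised at Visit 1 before the first fitting (5.1), so a Test-first subject already belongs to a sequence when the Test lens goes in (step 1.16) and its fit is graded (step 1.23).

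- **Visit 1 (7.2).** If the fit is graded unacceptable at step 1.23, "then the subject is discontinued from the study and will not be replaced". Step 1.24, which comes before dispensing, requires: "The lens fit is acceptable OD and OS".
- **Withdrawal (8.2).** One listed reason is "Subject not successfully dispensed due to lack of efficacy and safety including poor vision, poor comfort or unacceptable fit".
- **Disposition (8.1).** Item 4(iii) classes subjects as Enrolled not Successfully Dispensed "if they are randomized but did not satisfactorily complete the dispensing process". Item 7 then says "Safety and efficacy analysis sets will be defined as subsets of dispensed subjects (Completed + Discontinued", and the item 4 category lies outside those two groups.
- **Populations (14.3).** Safety is "All subjects who were administered any test article" and ITT is "All randomized subjects regardless of actual treatment and subsequent withdrawal from study or deviation from protocol", each with at least one observation recorded. Per-Protocol requires all visits to be completed.
- **Endpoint (2.2, 2.3).** Fit is assessed at all scheduled visits, and the hypothesis covers all subjects wearing the Test lens, with a bar of 90%.
- **Analysis (14.5).** The fit model, priors and success rule are given (lower 95% credible bound above 0.90), but no population is. Section 14.1 covers summaries only, and refers to an analysis population that is not defined.
- **Precedence (14.3).** A separate SAP is announced and, where they differ, "the SAP will supersede the statistical sections in the protocol". It is not among the documents reviewed.

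**The concern.** The subjects whom item 7 removes for unacceptable fit are selected by the outcome being tested. After that removal, every remaining Test-first subject has an acceptable Visit 1 fit by construction. Fit acceptance is a primary hypothesis against a fixed 90% bar, and 2.3 makes study success depend on all primary and secondary hypotheses. No Control-group comparison is involved, so nothing offsets the loss. With no population named in 14.5, three sets are open: the 14.3 Safety or ITT set, which counts these failures, and the item 7 set or Per-Protocol, which do not.

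**Working it through.** **1. Trace one subject.** Test-first, randomised, Test lens inserted, one eye graded unacceptable at step 1.23.

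| Rule | Is the failure counted? |
|---|---|
| 2.2 and 2.3 | Yes: Visit 1 is a scheduled visit and the Test lens was worn |
| 14.3 Safety, ITT | Yes: lens administered, randomised, one observation recorded |
| 14.3 Per-Protocol | No: visits not completed |
| 8.1 items 4(iii) and 7 | No: outside Completed + Discontinued |
| 14.5 | Not stated |

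**2. The plan's own figure.** Table 7 gives 83% power with 70 subjects for fit (95% against 90%, 14.2). With correlations 0.80 within and 0.50 across periods, 35 Test-first subjects give 2 eye-period records each (variance factor 2 + 2×0.80 = 3.6). The 35 Control-first subjects give 4 each (4 + 2×(2×0.80 + 4×0.50) = 11.2). Effective n = 210²/(35×3.6 + 35×11.2) = 44,100/518 = 85.1. Wald power at one-sided 0.025 = Φ(0.05/√(0.95×0.05/85.1) − 1.96) = Φ(0.16) = 56%. Other closed-form variants using these correlations and 70 subjects give 25% to 78%. The figure is not reproduced. It is not called wrong, because the simulated model and sidedness are not given, and this point does not depend on it.

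**3. How many subjects.** At eye-level acceptance p and between-eye correlation 0.80, P(at least one eye fails) = 1 − [p² + 0.80p(1 − p)]. At p = 0.95 this is 1 − 0.9405 = 5.95%; at 0.90 it is 1 − 0.882 = 11.8%. With 65 Test-first subjects (half of 130), that is 3.9 and 7.7 subjects if all failures fall at Visit 1.

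**4. Shift in the rate.** Let a be true acceptance and s the share of Test-first failures that occur at Visit 1. Counting each subject once, with equal sequences, the expected reading is 2a/(2 − s(1 − a)).

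- a = 0.90: s = 0.25 gives 1.8/1.975 = 91.1%; s = 0.5 gives 1.8/1.95 = 92.3%; s = 1 gives 1.8/1.9 = 94.7%.
- a = 0.95, s = 1: 1.9/1.95 = 97.4%.
- a = 0.99, s = 1: 1.98/1.99 = 99.5%.

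**5. False success at a true 90%.** In the simplest model (60 per sequence, eyes alike, Beta(0.5, 0.5) prior), P(p > 0.90) ≥ 0.975 allows at most 5 failures among 120. With failures kept, P(Bin(120, 0.10) ≤ 5) = 1.6%. With all Test-first failures dropped, only Control-first failures count, and P(Bin(60, 0.10) ≤ 5) is about 44%.

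| Illustration | Kept | s = 0.25 | s = 0.5 | s = 1 |
|---|---|---|---|---|
| Exact, each subject once, 60 per sequence | 1.6% | 4.3% | 10.5% | 43.7% |
| Bayesian logistic, subject effect, the plan's priors and correlations | 1.6% | not run | 7.5% | 32% |
| Clustered simulation, the plan's correlations, logit interval, 65 per sequence | 2-3% | not run | not run | 17% |
| Same, Wald interval | 5% | not run | not run | 35% |

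With 65 per sequence the exact model gives 2.1%, 13.5% and 50.4% for kept, s = 0.5 and s = 1. The Bayesian illustration omits the site, eye, period, sequence and carry-over terms, and stops a subject after a failure.

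**6. At other rates.** At a true 95%, success is 44% kept, 70% (s = 0.5) and 92% (s = 1) in the exact model; 49%, 73% and 94% in the Bayesian model; and 56% kept against 80% (s = 1) in the clustered logit version. At a true 99%, the Bayesian model gives at least 99.9% throughout and the estimate moves by 0.2 to 0.4 points.

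**7. Stopping after a failed fit.** The clustered rows in step 5 do not stop subjects. If they do, a simple pooled rate at a true 90% reads 91.7% with everyone kept, and false success is about 10% (logit). With Visit 1 failures dropped as well, it reads 94.9% and 69%. The Bayesian model, which also stops subjects, does not show this pull when everyone is kept (mean estimate 89.0%). Whether it appears therefore depends on how the proportion is derived, which 14.5 does not say.

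**The case against.** The strongest defence is that item 7 sits in a disposition section and speaks of sets that will be defined, so 14.3 can be read as the operative definition. Naming a population is ordinary SAP content, and the unseen SAP may do it. Section 14.1 puts all variables on the Safety population, which under 14.3 would at least show these failures. The historical fit data are redacted, 14.2 calls 95% a conservative reference, and 90% is the null rather than an expected value.

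Much of this stands. The documents do not show that the trial lacks a named population, nor that the decision would change. The conflict remains, however. Item 7 names both safety and efficacy sets, and the precedence clause covers the statistical sections, which does not plainly include section 8.

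A reader might infer three stronger things that the documents do not support:

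- **That only Test-first Visit 1 failures are lost.** Control-first subjects who fail at step 3.22 have already been dispensed a lens, which suggests this. But reasons (a)-(h) in 8.1 item 2 do not list unacceptable fit, and item 4(iii) is not limited to Visit 1, although lenses are also dispensed at Visits 3 and 4. The status of later failures is unclear.
- **That the false-success rate is near 44%.** That needs a true rate of exactly 90%, every failure at the first fitting, and eyes that behave alike.
- **That keeping these subjects makes the fit test unbiased.** Step 7 of the working shows that it may not.

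**Conclusion.** The point holds. Item 7 contradicts the 14.3 Safety and ITT definitions, and following it removes recorded failures of a primary endpoint in at least one identifiable group. The upward direction follows from the text, because subjects are removed for failing. The size rests on assumed failure rates and timing, about 60 to 65 subjects per sequence, and simplified stand-ins for the 14.5 model. At a true 90%, false success goes from about 2-3% to about 4-10% if a quarter to half of Test-first failures occur at Visit 1, and to roughly 17-44% if all do. The Wald row starts higher, at 5%, and the exact model with 65 per sequence runs above these ranges. Near 99% nothing of consequence changes.

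**What to change.** 1. Amend 8.1 item 7 so that it does not override the Safety and ITT definitions in 14.3.
2. State in 14.5 that fit acceptance is tested in all randomised subjects in whom a Test lens was placed and the fit graded, whether or not it was dispensed. If the separate SAP already names the population, align 8.1 and 14.5 with it.
3. Say in 8.1 where subjects stopped for unacceptable fit at Visit 3 or later are classed. Once 14.3 governs the analysis sets, this affects only the disposition table.

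No new data are needed, since the grades are recorded at step 1.23. The change does have a price: the reported rate and the chance of declaring success may be lower than under item 7. At a true 95%, the Bayesian illustration falls from 73% (half of Test-first failures at Visit 1) or 94% (all) to about 49%. That is no added cost if the 14.3 ITT set was intended all along. The change does not by itself remove any upward pull from stopping subjects after a failed fit, so the report should say how the proportion was derived from the model.
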